3. STUDY DESIGN

One of the aims of this placebo-controlled, randomized, double-blinded study is to determine the efficacy of antiseptic mouthwashes on reducing SARS-CoV-2 cellular infectivity in COVID+ patient saliva (described above). Asymptomatic and symptomatic SARS-CoV-2+ subjects will be enrolled in the study (according to Inclusion and Exclusion Criteria - Section A.3). Symptomatic SARS-CoV-2+ subjects will be enrolled within 10 days of symptom onset and/or within 10 days of initial positive test; asymptomatic SARS-CoV-2+ subjects will be enrolled within 10 days of initial positive test. Positive test results will be accepted if they are provided by a medical professional or official testing site. Results can appear either in the UNC electronic medical record or be printed from an established testing site such as UNC, a local pharmacy, a medical practice, or an established lab. At-home positive test results will be accepted when they are confirmed by study

personnel with a rapid antigen test at the time of visit. Subjects will be seen and samples collected in the isolated Clinical Research Space associated with the GoHealth Clinic (Adams School of Dentistry, UNC Chapel Hill, North Carolina, USA). SARS-CoV-2+ subjects will be enrolled within 10 days positive test. Study participants who meet all inclusion criteria without any exclusion criteria will be randomized to either an experimental or control group using a block randomization tool.

Participants will be asked to give a baseline salivary sample (5ml over 5 minutes) and then asked to rinse with an unlabeled (blinded) antiseptic mouth rinse for 60 seconds according to the table below. The rinses and control will be similar in appearance visually, such that a double-blind can be maintained. The research assistant ([name]) will be the sole unblinded staff member who will perform randomization and communicate the subject's group assignment to blinded study staff, in advance of the visit based on the block randomization schedule. The unblinded staff member will set-up the rinses for the participants appointment minimizing the possibility of study staff being able to identify the blinded rinses. In the instance that [name] is unavailable, [name] or [name] will perform randomization and set-up the rinses. Blind will be strictly maintained except in the case of medical emergency requiring reveal of an individual's rinse identity. The product group key will be provided to the analyzing statistician at the conclusion of the clinical study.

mouth rinse*	Number of participants (sample size)	Group
26.9% ethanol plus essential oils	84	Experimental
0.1% Cetylpyridinium Chloride	84	Experimental
Sterile water	84	Control

**All mouth rinses are commercially available in the USA, routinely used in clinical settings, and will be used in an on-label manner.*

After the participant expectorates the mouth rinse, research staff will collect another salivary sample (T_0 , 2 mL over 5 minutes). During a 10 minute recuperation period, the study participants will answer demographics survey questions and questions regarding the taste, color, flavor and general acceptability of using the mouth rinse as part of routine dental and medical visits as well as in social settings. At 15 minutes post-rinse, the participant will be asked to provide an additional saliva sample (2 mL over 5 minutes), followed by another 10 minute recuperation period. This sequence will be repeated for at

the 30, 45 and 60-minute time points post rinse. At 60 minutes, the study participant will give their final salivary sample (2 mL over 5 min), and study participation will conclude.

All salivary samples will be collected on ice in sterile 15 mL conical vials labelled “COVID Core” and using pre-printed labels including patient’s random alphanumeric study ID. Saliva samples will be cataloged and stored at the UNC Delta COVID Translational Initiative (also known as the Covid-19 Core) for future qRT-PCR and viral infectivity assays. Samples will be transported on ice from the collection site to 4403A Koury Hall in leak proof biohazard bags. Samples will be processed according to the **sample processing and outcomes** procedure (below).

Following study participation completion, participants will receive \$50 compensation in the form of a Visa gift card.

During the period that the COVID+ study participants are present in the clinic and giving saliva samples, we will inquire about their comfort. If participants exhibit signs of distress, research study staff will contact emergency medical responders (present in the building) to visit the patient and if deemed appropriate, the participants will be escorted to UNC hospital (adjacent building).

This time course analysis design will allow us to determine if any of the antiseptic mouthwashes are effective at reducing SARS-CoV-2 in salivary secretions of COVID-19+ study participants as well as to determine the therapeutic window if effective. We have designed this study to recapitulate a standard oral exam and procedure time (~1 hr in length). Further, the design will allow for a kinetic analysis of viral shedding in salivary secretions and to determine the most effective mouth rinse.

Sample processing and outcomes

Sample processing: Following collection, saliva samples will be processed according to existing BSL2+ SOP protocols (COVID Core, UNC (PI: [name] and [name]) by pre-authorized personnel. Samples will be assessed for **1**) molecular presence of SARS-CoV-2, **2**) salivary antibody and cytokine responses to SARS-CoV-2 and **3**) in vitro infectibility. All samples have labels with only alphanumeric identifiers thus maintaining the blind and protecting PHI through the entire laboratory analysis process.

1. Molecular analysis: For molecular analysis, samples will be inactivated by adding 2 mL of extraction buffer to each 500 uL saliva aliquot (4:1 ratio) and mixed by inversion. These samples will be further aliquoted at 250uL in 1.5 mL Eppendorf tubes and stored in an “Inactivated Samples -80 °C Freezer” until further analysis.

2. Antibody and cytokine responses: an aliquot of saliva will be inactivated in a 56 °C water bath for 30 minutes. 250 uL aliquots will be transferred into 1.5 mL cryovials and

stored in the “Inactivated Samples -80 °C Freezer” in 4403A Koury Hall until further analysis.

3. In vitro infectivity: Samples will be stored in the “Activated Samples -80 °C Freezer” in 4403A Koury Hall until further analysis.

At analysis, all samples will be serially diluted in sterile PBS (10⁻¹⁰ fold dilutions). Plaque assays will be performed using Vero E6 cells at confluence in 96-well cell culture plates. Briefly, cell cultures will be washed with sterile PBS and samples containing virus will then be plated in duplicate (100 µL per well). Plates will be incubated at 37 °C for 45 minutes with occasional rocking. Then 2 mL of 0.5% agarose in minimal essential media (MEM) containing 2% FBS and antibiotics will be added per well. Plates will be incubated at 37 °C for 72 hours, fixed with 10% buffered formalin, followed by the removal of the overlay, and then stained with 0.2% crystal violet to visualize plaque forming units (PFU). Average PFUs will be evaluated by OD. All assays will be performed in BSL-3 laboratory setting. (PMID: 32475066)

Unprocessed saliva exceeding immediate experimental capacity will be stored in aliquots of 250 uL volume in 1.5 mL Eppendorf tubes and stored in “Activated Samples -80C Freezer.”

Survey data: The survey data will be analyzed and used to determine clinical and other factors impacting applicability of each of the mouth rinses.

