4.2 Exclusion Criteria

Subjects presenting with any of the following will not be included in the study:

- Patients who have been eating or drinking within an hour of the study
- Patients under 18 years old and older than 65 years old
- Subjects presenting with and/or self-reporting any of the following will not be included in the study:
 - history of significant adverse effects following use of oral hygiene products such as toothpastes and mouth rinses. (self-reported)
 - Self-reported allergy to ethanol, essential oils (Eucalyptol, Menthol, Methyl salicylate, Thymol), Listerine, Cetylpyridinium Chloride, and other components in the mouth rinses.
 - History of serious medical conditions that, at the discretion of the Investigator, will disqualify the subject. (Self-reported)
 - A history of severe dry mouth (xerostomia), severe drug-induced xerostomia (antidepressants, anticonvulsants, antihypertensives), or Sjogren's syndrome
 - A history of recent (within the last 30 days) or current **recent oral herpes flare up**, candida (thrush) infection, aphous ulcer flare up, current/active severe periodontal disease, or other recent oral viral infection or flare up within the past 30 days (self-reported)
 - Current history of alcohol or drug abuse (self-reported).
 - History of drinking water or eating food within an hour of the study visit.
 - History of drinking alcohol within 12 hours of the study visit.
 - History of using a commercial mouth rinse within 24 hours of the study visit.
 - Participation in any study involving oral care products, concurrently or within the previous 30 days. (self-reported)
 - Positive pregnancy test, reported pregnancy or lactation (this criterion is due to oral tissue changes related to pregnancy and nursing which can affect interpretation of study results. Additionally, women are advised to check with their physician before using Ethanol rinses during pregnancy and lactation, which cannot occur in a blinded, randomized trial.)
 - Other severe acute or chronic medical or psychiatric condition or laboratory abnormality that may increase the risk associated with trial participation or investigational product administration or may interfere

with the interpretation of trial results and, in the judgment of the Investigator, would make the subject inappropriate for entry into this trial.

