- Patient with developmental/cognitive disability that cannot self-consent, comprehend and follow the requirements of the study based on research site personnel's assessment.
- Patients with sizable mucosal tears, abrasions, growths or burns in the mouth
- The following table lists exclusion criteria specific to each mouth rinse proposed in the study:

mouth rinse*	Exclusions
26.9% ethanol plus essential oils	
 ● Do not use in children under 12
0.1% Cetylpyridinium Chloride	
 ● Do not use in children under 6
Sterile Water	No contraindications

**All mouth rinses are commercially available in the USA, routinely used in clinical settings, and will be used in an on-label manner.*

Summary of Inclusion and Exclusion Criteria for Mouth rinse RCT

Inclusion Criteria	Exclusion Criteria
Individuals (all sex, all gender) at least 18 years of age and at most 65 years of age in good oral health and with stable physical health, decided at the discretion of the study coordinator.	Known allergies or significant adverse reactions following the use of oral hygiene products (toothpastes, mouth rinses), commercial cosmetics, iodine, and any ingredient in the mouth rinses (list will be provided).

Diagnosed COVID+ status by physician, official testing site, or on-site rapid antigen test administered by study personnel at the time of visit. Either became symptomatic or initially tested positive in the prior 10 days.
	
Established history of severe Xerostomia (drug-induced or autoimmune dry mouth), severe periodontal disease with actively bleeding gums, significant oral abrasions/ulcers or growths, alcohol abuse, and/or recreational drug abuse. Other severe acute or chronic medical or psychiatric condition or laboratory abnormality that may increase the risk associated with trial participation or investigational product administration or may interfere with the interpretation of trial results and, in the judgment of the Investigator, would make the subject inappropriate for entry into this trial.

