At the visit, a consented patient will answer screening questions regarding inclusion and exclusion criteria. Answers will be entered into the CDART research database managed by UNC. Participants lacking a lab or physician confirmed COVID+ test will be administered a rapid antigen test by study personnel at the time of their visit to confirm their COVID infection. Any participants that produce a negative rapid antigen test (on-site) will be excluded. Prior to finalizing these screening questions, women participants of childbearing potential will be asked to provide a urine sample in the restroom, to undergo a rapid pregnancy test by study personnel. Any pregnant or lactating patients will be excluded.

Our study statistician, [name], will create a block randomization schedule and perform these computations. All patients will be consented and then fill out our screening questions for inclusion and exclusion to confirm eligibility prior to being assigned to the randomization schedule.

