6. STUDY PROCEDURES

6.1 Schedule of Evaluations

Assessment	Phone Screening: (Day-14 to Day -1)	Final Screening, Baseline, Enrollment, Randomization, Intervention: Visit 1 (Day 0)
Informed Consent Form	Provided for review	X
Demographics		X
DXA	X verbally asked	X
Medical History		X
Current Medications		X
Rapid Antigen Test-COVID+		X

Urine Analysis- pregnancy		
Vital Signs		
Inclusion/Exclusion Criteria	 reviewed	
Enrollment/Randomiz- ation		
Treatment Administration Form		
Concomitant Medications		
Adverse Events		

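### Section 3 has participants randomised and their assignment passed on before the visit, but the consent and confirmed eligibility that must come first are settled only at the visit

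*Combined protocol and SAP*

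**What the plan says.** Section 3 (Study Design) makes one research assistant, with named backups, responsible for randomising and for setting up the rinses. That person is to communicate the subject's "group assignment to blinded study staff, in advance of the visit based on the block randomization schedule".

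The sections on enrolment, randomisation and consent give a different order. In section 4.3 patients are consented and then "fill out our screening questions for inclusion and exclusion to confirm eligibility prior to being assigned to the randomization schedule". Sections 6.2.2 and 11.2 repeat that order in nearly the same words. Section 9.2 has the unblinded staff member randomise after enrolment compliance is confirmed and consent obtained, and only then pass the assignment to blinded staff.

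The schedule in section 6.1 puts these steps in one column, headed "Final Screening, Baseline, Enrollment, Randomization, Intervention: Visit 1 (Day 0". Section 6.2.1 says that screening is completed at Visit 1.

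**The concern.** Randomisation protects a comparison only if nobody who decides on entry can know, or be influenced by, the next assignment. The usual safeguard is to assign last, after consent is signed and eligibility is fixed. Section 3 reverses that order for the individual participant.

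Two things would be at stake if staff worked from Section 3.

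- **Concealment.** Some entry decisions here rest on judgement. One exclusion is "History of serious medical conditions that, at the discretion of the Investigator, will disqualify the subject", and the summary table asks for "stable physical health, decided at the discretion of the study coordinator". A study coordinator also conducts the consent process (section 6.2.1). If the people making these calls already held the assignment, entry could depend on it.
- **People assigned but never enrolled.** Someone randomised beforehand may decline to sign, or may fail the on-site antigen or pregnancy test. Sections 6.2.5 and 8 list loss of eligibility as a possible reason for discontinuation, but they provide for replacement only when saliva is insufficient. Section 9.3 describes who is eligible and defines no analysis set. The plan therefore does not say whether such a person counts as randomised or what happens to the used place in the block.

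**Working it through.** The point concerns the order of events, so no arithmetic applies. The relevant places, side by side:

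| Place | When randomisation happens | Is the visit stated there? |
|---|---|---|
| Section 3, paragraph on rinsing and blinding | Before the visit, with the assignment passed on | Yes, as an event still to come |
| Section 4.3 | After consent and confirmed eligibility | Yes: screening questions are answered at the visit |
| Section 6.2.2 | After consent and confirmed eligibility | Outpatient consent is signed in person in the research core |
| Section 9.2 | After enrolment compliance is confirmed and consent obtained | No |
| Section 11.2 | After consent and confirmed eligibility | Yes: screening questions are answered at the visit |
| Section 6.1 | Listed in the Visit 1, Day 0 column | Yes |
| Section 6.2.1 | Not stated; outpatient consent is signed in person and screening is finished at Visit 1 | Yes |

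The opening of Section 3 also says that participants "who meet all inclusion criteria without any exclusion criteria will be randomized to either an experimental or control group". That agrees with the later sections by inference only, because it does not date the step.

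The reasoning runs in three steps.

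1. Four sections (4.3, 6.2.2, 9.2, 11.2) require both consent and confirmed eligibility before assignment.
2. Eligibility cannot be confirmed before Visit 1. Section 6.2.1 completes screening there, and sections 4.3 and 6.2.1 do the antigen and pregnancy tests on site. Outpatients also sign consent there. Section 9.2 does not give the visit timing itself; the timing comes from the other sections.
3. Assignment therefore cannot precede the visit and also satisfy step 1. The Section 3 statement and the four sections cannot all be followed.

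Three readings might rescue Section 3, and none does.

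- *Only the schedule is prepared early.* The sentence concerns the individual subject's assignment, not the list.
- *Eligibility is settled at the phone screen.* Inclusion and exclusion criteria are reviewed by phone, but section 6.2.1 calls this prescreening.
- *In-patients may sign earlier.* Their consent could come shortly before the study procedures, but their screening still ends at Visit 1, and Section 3 is not limited to in-patients.

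**The case against.** The strongest reply is that Section 3 contains one stray phrase. The procedural sections and the schedule all give the right order, so staff would probably follow those. Harm to concealment also needs a further step that the documents do not supply: that the blinded staff who are told are the ones who take consent or judge eligibility. In addition, every participant gives a pre-rinse sample, the reduction factor compares titre before and after the rinse, and section 9.5 plans ANCOVA on change. A baseline difference between arms would therefore act less directly than on an unadjusted post-rinse comparison.

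Much of this stands, and it is why no bias is asserted. It does not remove the contradiction. Section 3 is where the preparer's task is set out in operational terms, and its instruction can be carried out as written.

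A reader might infer more: that the clinic blind is broken because blinded staff learn the arm, or that they could work out an arm code from answers to "questions regarding the taste, color, flavor and general acceptability of using the mouth rinse". The documents do not support this. The recipients are described as blinded, the set-up is meant to limit recognition of the rinses, and "The product group key will be provided to the analyzing statistician at the conclusion of the clinical study". That suggests a coded assignment, although no section says so. No section says that the assignment names a product or that one code is reused for each arm.

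A reader might also see a conflict between the unlabelled containers and the numerical code in section 9.2. The plan uses unlabelled and blinded as near-synonyms, so a container with a code but no product name fits both.

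**Conclusion.** The timing conflict is certain on the text: one statement in Section 3 against four sections, with sections 6.1 and 6.2.1 supporting the four by schedule. The statement should be corrected, because followed as written it assigns participants before consent and eligibility are settled.

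The consequence for concealment is conditional on consenting or screening staff receiving the assignment, which Section 3 leaves open. The consequence for people who decline or fail on-site screening does not depend on that: they would already be assigned.

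No size of bias is claimed, and none can be derived from the documents. The antigen and pregnancy exclusions are objective tests. The laboratory blind is untouched, since Section 3 has samples carry only alphanumeric identifiers. Section 3 may be a drafting slip rather than an intended procedure, but the correction is the same either way.

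**What to change.** In Section 3, strike the phrase that places randomisation and communication ahead of the visit. State instead that randomisation, and any communication of the assignment, takes place only after consent and confirmed eligibility at Visit 1. That agrees with sections 4.3, 6.1, 6.2.2, 9.2 and 11.2, none of which needs to change for this purpose.

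Rinses can still be prepared beforehand in coded containers, provided that a container is allocated in sequence only once eligibility is confirmed.

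The cost is a wording change and one practical constraint. Unless containers are prepared in advance, the unblinded preparer or a backup must be available at each visit, including visits held in a hospital room (sections 4.3 and 6.2.1). The preparer and the backups are already provided for in Section 3.

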6.2.2 Enrollment, Baseline, and/or Randomization

Enrollment

Outpatient subjects will be recruited from patients seen in the UNC Respiratory Diagnostic Clinic (RDC), UNC testing sites or UNC hospital who have tested positive for COVID-19. Subjects will be contacted for recruitment by phone and (if unreachable by phone) by secure email by study personnel; patients will have the study rationale and risks explained and will be provided time to ask questions and consider participation. If patients are interested in participating, a single appointment will be scheduled for them at the Adams School of Dentistry Go Health Clinical research core in the associated clinical research isolation area. Consent documentation will be signed in person and in private in the Clinical Research Core. A list of COVID+ subjects will be provided by the RDC clinic and EPIC, accessible via secure UNC servers or secure UNC email to our research team's clinical coordinator, and this list will include names and contact details (PHI). This list is updated daily and provided to approved research sites, including ours.

Baseline Assessments

Study personnel confirm enrollment qualifying criteria and perform a COVID rapid antigen test and pregnancy test on applicable individuals. Otherwise, there are no baseline assessments required as this study only requires a 70-90 minute single visit appointment.

Randomization

Our statistician will create a block randomization tool which will be provided to the unblinded study staff ([name]) to perform the randomization. In the instance that [name] is unavailable, [name] or [name] will perform randomization and set-up the rinses. The participant's group assignment will be communicated to the blinded clinical staff. All patients will be consented and then complete our screening questions for inclusion and exclusion to confirm eligibility prior to being assigned to the randomization schedule.

The researcher in charge of collecting the salivary samples will be blinded to the mouthwash solution, as they will be given a pre-aliquoted mouth rinse in an unlabeled storage tube to provide to the patient for the rinse.

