6.2.3 Blinding

At their onsite visit, subjects will be provided with an unlabeled/blinded mouth rinse. The researcher in charge of collecting the salivary samples will be blinded to the mouthwash solution as well, as they will be given a pre-aliquoted mouth rinse in an unlabeled storage syringe to provide to the patient for the rinse. Our statistical consultant, [name], will set up a randomization schedule that the team will abide by for assignment of enrolled subjects.

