9. STATISTICAL CONSIDERATIONS

9.1 General Design Issues

A double-blinded, randomized controlled trial was chosen as the study design. It allows us to collect human based data on the effects of commercially available mouth rinses on salivary infectivity and viral load. A crossover study was not pursued because the repeated use of different mouth rinses is likely to confound the results. A 1-hour time-course was chosen to correspond with the average length of most dental procedures. Fifteen minute intervals were chosen to evaluate viral kinetics over time, and to see when infectivity rebounds post- mouth rinse.

Statistical Hypothesis

The central hypothesis of this study is that a 60 second antiseptic mouth rinse will effectively reduce viral infectivity (>50%) of SARS-CoV-2 for a minimum of 30 minutes duration.

The secondary hypothesis is that a 60 second mouth rinse will be well tolerated in a clinical care setting by a majority of patients and providers.

Sample Size Considerations

Based on our similar viral load studies evaluating mouth rinse efficacy against SARS-CoV-2 and other enveloped viruses, we used power calculations to estimate effect size and determine sample size as a function of length of mouth rinse time course.¹² With simultaneous comparisons, the sample size n=43 for each mouth rinse can detect the effect size in Cohen's $d = 0.8$, which is between medium and large, under 80% power and 0.016 type-I error rate by Bonferroni correction.¹² To account for 14% of patients having no virus in their saliva and 10% of patients producing insufficient saliva, we plan to enroll 55 participants per arm.

Statistical analysis of our deidentified data will be performed by [name], the statistician on this project.

Primary Outcomes

The analyses will compare viral RNA level (qRT-PCR) and viral infectivity levels between mouth rinse types and across the time course

Data generated from the qRT-PCR assays will be presented as mean standard deviation for normally distributed data and as median [Interquartile range] for non-normally distributed data. P values will be reported as two tailed. Between group comparisons will be performed using a Student's t test or Mann-Whitney U test. Normality will be assessed using the Kolmogorov-Smirnov test, and logistic regression will be performed with robust standard errors.

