9.2 Sample Size and Randomization

Based on similar viral infectivity studies evaluating antiviral mouth rinse efficacy, we were able to run power calculations to estimate effect size and determine sample size as a function of length of mouth rinse time course. The sample size is justified by a paired t-test on outcomes between time points. With simultaneous comparisons, the sample size n=43 for each mouth rinse can detect the effect size in Cohen's $d = 0.8$ at 30 minutes, which is between medium and large, under 80% power and 0.016 type-I error rate by Bonferroni correction.¹² To account for 14% of patients having no virus in their saliva and 10% of patients producing insufficient saliva, we plan to enroll 55 participants per arm.

The statistical consultant on this project will create a block randomization tool for the study staff; the unblinded staff member will randomize a participant once enrollment compliance has been confirmed and consent has been given. The participant's group assignment will then be communicated to the blinded study staff. IRB approved study personnel will ask participants screening questions to confirm eligibility for enrollment. After consent and screening, the randomization tool will be used by study staff to assign the subject to a study group.

The researcher responsible for collecting the salivary samples will be blinded to the mouthwash solution, as they will be given a pre-aliquoted mouth rinse in an unlabeled tube to provide to the patient for the rinse.

The PI, Co-I, study coordinators and study personnel who work for GoHealth are authorized to break the blinding based on emergency medical necessity such as if a patient suffers an allergic or adverse reaction to one of the mouth rinses. Though highly unlikely as all mouth rinses are sold commercially at Walgreens and CVS, adverse or allergic reactions are possible. Using the numerical code associated with the participant and mouth rinse syringe, the study personnel responding to the emergency can reference the block randomization schedule to determine the mouth rinse type, to inform the emergency medical workers, poison control or the emergency room what type of mouth rinse product led to the reaction.

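### Withholding the product key from the analysing statistician gives no protection if that person also wrote a randomisation schedule that shows the rinse type

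*Combined protocol and SAP*

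**What the plan says.** Section 3 (Study Design) deals with unblinding in one paragraph. One research assistant "will be the sole unblinded staff member who will perform randomization". Two further people are to randomise and set up the rinses when the assistant is unavailable. On the analysis, the paragraph says: "The product group key will be provided to the analyzing statistician at the conclusion of the clinical study".

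The schedule is described in several places:
- **Section 4.3:** the study statistician "will create a block randomization schedule and perform these computations".
- **Section 6.2.2:** "Our statistician will create a block randomization tool which will be provided to the unblinded study staff".
- **Section 6.2.3:** a statistical consultant "will set up a randomization schedule that the team will abide by for assignment of enrolled subjects".
- **Section 9.2:** "The statistical consultant on this project will create a block randomization tool for the study staff".
- **Section 11.2:** again assigns the tool to the study statistician.

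On the analysis, Section 9.1 states "Statistical analysis of our deidentified data will be performed by" a person (name removed) described as the project's statistician. The survey is analysed separately by a consultant from another institute.

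On emergencies, Section 9.2 says that staff, using the code on the participant's syringe, "can reference the block randomization schedule to determine the mouth rinse type".

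**The concern.** Timing the release of a product key makes sense only if the recipient does not yet know which rinse is which. The text appears to give the schedule to the same person by another route, and Section 9.2 treats that schedule as enough to name the product.

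What is at stake is the freedom left to the analyst. Sections 9.1 and 9.5 allow a t test or a Mann-Whitney test, and the power paragraph of Section 9.5 adds ANCOVA without ranking it against them. Section 9.4.1 puts both infectivity and RNA level under the primary objective. There are several post-rinse times, and Sections 8 and 10.3.3 keep participants with deficient 45- or 60-minute samples without saying how the analysis handles them. An analyst who knows the products makes these choices with the commercial identity of each arm in view. That is what a withheld key would normally prevent.

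**Working it through.** No arithmetic applies. The check is whether the sections can all be true together and still leave the analyst unaware of the products.

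**1. Who writes the schedule?** Sections 4.3 and 11.2 say the study statistician, and Section 6.2.2 says the statistician. Sections 6.2.3 and 9.2 say a statistical consultant.

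**2. Who analyses the virological data?** The project's statistician (Section 9.1). The personnel list before the Précis shows two statisticians, one of them marked for survey data. The natural reading is that the other does both jobs. No section names a separate author for the schedule or describes a barrier between schedule and analysis.

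**3. What does the schedule contain?** The documents point both ways.
- Section 3 speaks of a product group key, and Sections 3 and 6.2.2 have the group assignment passed to blinded staff. Those staff stay blinded only if the group is a code. This suggests coded arms with a separate key.
- Section 9.2 has responders read the rinse type from the schedule, with no mention of a key. This suggests that the schedule carries products.

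**4. Does withholding the key work?**

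| Schedule shows | Author is the analyst | Author is not the analyst |
|---|---|---|
| Products | No: the analyst's own schedule does what the key would do | Yes, if the schedule is kept from the analyst |
| Arm codes only | Yes, until the key is released | Yes, until the key is released |

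The safeguard fails in one of the four cells. That cell is where the plainest reading of Sections 4.3, 9.1, 9.2 and 11.2 leads. If the schedule is coded, the safeguard survives but the emergency procedure in Section 9.2 does not work as written, because the schedule alone would not name a product. So either Section 9.2 needs rewording, or the roles of author and analyst must be separated in the text.

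**5. When is the key released?** At the conclusion of the clinical study, which is not defined. Participation ends with the 60-minute sample (Section 3). Section 9.4 says the assays are run in large batches, with results weeks to months after collection. If the clinical study ends with the last visit, the key is handed over before the last assay and before the analysis choices are made. In that case the safeguard lapses early even in the favourable cells.

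**6. Who is unblinded?** By the plan's own account, the assistant and, when they act, the two backups. If the schedule shows products, its author is unblinded as well. The description "will be the sole unblinded staff member who will perform randomization" counts only the first.

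**The case against.** Several parts of the case on the other side stand, and they limit the point.

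- **A reader might infer that the plan promises a blinded analysis and breaks the promise.** It does not promise one. Section 3 only times the hand-over of the key, and Section 9.4 openly says that the committee judging the results is not masked.
- **A reader might infer that the analyst holds every participant's product from the first day.** This is not shown. Nobody has been assigned then, Section 6.2.2 passes the tool to unblinded staff who make the assignments, and samples and data carry a random study ID (Sections 3 and 10.2). No section gives the statistician the completed participant-level list. The emergency look-up belongs to the investigators, coordinators and clinic staff.
- **A reader might want to attach an inflated type I error to this flaw.** Picking the most favourable of several tests needs only group labels, so an analyst working with A, B and C could do the same. Such a figure would measure an insufficiently specified primary analysis, which is a separate matter. Sections 9.1 and 9.5 also provide a Kolmogorov-Smirnov normality check, so t test versus Mann-Whitney need not be a free choice.
- **That author and analyst are one person is inferred.** Names are removed, job titles vary, the survey analyst is also called a statistical consultant, and the personnel list may be incomplete in the text available.
- **The backups are disclosed** in the same paragraph as the claim of a single unblinded person, so that wording is inaccurate but conceals nothing.
- **Measurement is protected separately.** The saliva collector is to be blinded (Sections 6.2.2, 6.2.3 and 9.2), and laboratory labels are coded (Section 3).

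None of this reconciles Section 3 with Section 9.2.

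**Conclusion.** The point holds in a limited form. The safeguard in Section 3, no product key for the analyst until the clinical study ends, is ineffective as described if two conditions hold: the schedule shows the rinse type, as Section 9.2 says, and its author is the analyst, as the role descriptions suggest. The second is an inference that the sponsor can confirm or correct at once. Separately, the release point is undefined and may come before the assays and analysis.

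The consequence is qualitative: the analyst may know the products while analysis choices remain open. The documents give no basis for a numerical bias, and none is claimed. Blinding of participants, saliva collectors and laboratory is not put in doubt by this point. The change is worth making because it restores a protection that the plan evidently intended and costs almost nothing.

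**What to change.** 1. Have the statistician issue the block schedule in arm codes only (A, B, C), and say so in Sections 4.3, 6.2.2, 6.2.3, 9.2 and 11.2, using one title for the role throughout.
2. Have the unblinded assistant and the named backups hold a separate code-to-product key, and state that it is accessible for emergency unblinding.
3. Reword Section 9.2 so that emergency look-up goes from the participant's code through that key and no longer relies on the schedule alone.
4. In Section 3, replace the present release point with one after the last assay, database lock and dated analysis code.
5. State whether the schedule's author and the analyst are the same person. Replace the reference to a single unblinded person with a list: the assistant, the two backups, and the schedule's author for as long as the schedule shows products.

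The cost is protocol wording and a coded list. The one practical downside is the changed emergency route: the key must be reachable when the assistant is away, so cover has to be written in. Coded arms do not settle which analysis is primary. The dated analysis code in step 4 is what fixes the open choices before the products are known.
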